### Dose Reduction(s) for Q2W Dosing Schedule

If dose reduction is required during the Q2W dosing period, U3-1402 dosing should be reduced by 1 dose level (Table 5.1); all subsequent cycles during the Q2W dosing period should be administered at the reduced dose level and the equivalent Q3W dosing level should be used from Cycle 4 and beyond, unless further dose reduction is required.

Table 5.1: Dose Levels for U3-1402

Dose Level	Q3W Dose Schedule (21-day cycles)	Q2W Dose Schedule (14-day cycles)
1 a	1.6 mg/kg IV infusion Q3W	1.0 mg/kg IV infusion Q2W
2	3.2 mg/kg IV infusion Q3W	2.1 mg/kg IV infusion Q2W
3	4.8 mg/kg IV infusion Q3W	3.2 mg/kg IV infusion Q2W
4	6.4 mg/kg IV infusion Q3W	4.2 mg/kg IV infusion Q2W
5	8.0 mg/kg IV infusion Q3W	5.3 mg/kg IV infusion Q2W
6	9.6 mg/kg IV infusion Q3W	6.4 mg/kg IV infusion Q2W

IV = intravenous; Q2W = once every 2 weeks; Q3W = once every 3 weeks.

<sup>a Dose reductions below Dose Level 1 will not be permitted.

Table 5.2: Dose Delay Criteria and Dose Reduction for U3-1402

	Worst Toxicity NCI- CTCAE Version 5.0 Grade (unless otherwise specified)	Schedule Modification for U3-1402	
General disorders an	General disorders and administration site conditions		
Infusion related reaction	Grade 1 Mild transient reaction; infusion interruption not indicated; intervention not indicated	If infusion related reaction (such as fever and chills, with and without nausea/vomiting, pain, headache, dizziness, dyspnea, hypotension) is observed during infusion, the rate should be reduced by 50% and subjects should be closely monitored.  If no other reactions appear, the subsequent infusion rate could be resumed at the initial planned rate.	
	Grade 2 Therapy or infusion interruption indicated but responds promptly to symptomatic treatment (eg, antihistamines, NSAIDs, narcotics, IV injection fluids); prophylactic medications indicated for ≤24 hours	U3-1402 infusion should be interrupted. Symptomatic treatment (eg, antihistamines, NSAIDs, narcotics, IV fluids). If the event resolves or improves to Grade 1, infusion can be re-started at a 50% reduced infusion rate. Upon restart, if Grade 2 symptoms recur, no further U3-1402 should be administered at that visit. The amount of U3-1402 infused must be recorded in the eCRF. Subsequent infusions must be conducted at the 50% reduced infusion rate (ie, same reduced rate as previous infusion).	
	Grade 3 Prolonged (eg, not rapidly responsive to symptomatic medication and/or brief interruption of infusion); recurrence of symptoms following initial improvement; hospitalization indicated for clinical sequelae  Grade 4 Life-threatening consequences; urgent intervention indicated	Administration of U3-1402 should be discontinued immediately and permanently.  Urgent intervention indicated. Antihistamines, corticosteroids, epinephrine, bronchodilators, vasopressors, IV fluid therapy, oxygen inhalation etc, must be administered as clinically indicated.	
Fatigue/ Asthenia	Grade 3	Delay dose until resolved to ≤Grade 1 or baseline values, then:  If resolved to ≤Grade 1 or baseline values in ≤14 days, resume U3-1402.  If resolved to ≤Grade 1 or baseline values in >14 days, U3-1402 may be resumed after discussion and agreement reduce U3-1402 by 1 dose level and resume.	
Blood and lymphatic			
Neutrophil count decreased	Grade 3 (500 to <1000/mm  ; 0.5-1 × 10  /L)	Delay dose until resolved to ≤Grade 2, then resume U3-1402.	
a contract	Grade 4 (<500/mm  ; <0.5 × 10  /L)	Delay dose until resolved to ≤Grade 2, then reduce U3-1402 by 1 dose level.	

Table 5.2: Dose Delay Criteria and Dose Reduction for U3-1402 (Continued)

	Worst Toxicity NCI- CTCAE Version 5.0 Grade (unless otherwise specified)	Schedule Modification for U3-1402
Febrile neutropenia (ANC <1000/mm³;	Grade 3	Delay dose until resolved; then resume U3-1402. Consider reducing U3-1402 by 1 dose level.
<1 × 10  /L, fever >38.3°C or a sustained		Consider administration of granulocyte colony-stimulating factor as prophylaxis for all subsequent cycles and according to local guidelines.
temperature of ≥38°C for more	Grade 4	Delay dose until resolved, then reduce U3-1402 by 1 dose level and resume.
than 1 hour)		Administer granulocyte colony-stimulating factor as prophylaxis for all subsequent cycles and according to local guidelines.
Anemia	Grade 3 (Hemoglobin <8.0 g/dL)	Delay dose until resolved to ≤Grade 2 or baseline; then resume U3-1402.
		For recurrent anemia, delay dose until resolved ≤Grade 2 or baseline, then reduce U3-1402 by 1 dose level and resume.
		Consider packed red blood cell transfusion according to institutional guidelines.
	Grade 4 (Life-threatening consequences; urgent intervention indicated)	Delay dose until resolved to ≤Grade 2 or baseline, then reduce U3-1402 by 1 dose level and resume.  Consider transfusion according to institutional guidelines.
Platelet count decreased	Grade 3 (Platelet <50 - 25 × 10  /L)	Delay dose until resolved to ≤Grade 1, then:  If resolved in ≤14 days, resume U3-1402.  If resolved in >14 days, U3-1402 may be resumed.  Consider reducing U3-1402 by 1 dose level.  Consider platelet transfusion according to institutional guidelines.
	Grade 4 (Platelet <25 × 10  /L)	Delay dose until resolved to ≤Grade 1, then reduce U3-1402 by 1 dose level and resume.  Consider transfusion according to institutional guidelines.
Lymphocyte Count Decreased	Grade 4 (<0.2 × 10  /L)	Delay dose until resolved to ≤Grade 2, then: If resolved in ≤14 days, resume U3-1402. If resolved in >14 days, reduce U3-1402 by 1 dose level and resume.
Cardiac disorders		
Heart failure	Grade ≥2 (Symptoms with moderate activity or exertion)	Cardiologist consult as necessary.  Delay dose until resolved to ≤Grade 1, then reduce U3-1402 by 1 dose level.
Ejection fraction decreased	Decrease in LVEF 10% to 20% (absolute value), but LVEF >45%	Continue treatment with U3-1402.
	LVEF 40% to ≤45% and decrease is <10% (absolute value) from baseline	Continue treatment with U3-1402. Repeat LVEF assessment within 3 weeks.

Table 5.2: Dose Delay Criteria and Dose Reduction for U3-1402 (Continued)

	Worst Toxicity NCI- CTCAE Version 5.0 Grade (unless otherwise specified)	Schedule Modification for U3-1402
	LVEF 40% to ≤45% and decrease is ≥10% to 20% (absolute value) from baseline	Delay U3-1402 dosing. Repeat LVEF assessment within 3 weeks. If LVEF has not recovered to within 10% (absolute value) from baseline, discontinue subject from study treatment.
	LVEF <40% or >20% drop from baseline	Delay U3-1402 dosing.  Repeat LVEF assessment within 3 weeks; if LVEF <40% or >20% (absolute value) drop from baseline is confirmed, discontinue U3-1402.  Cardiologist consult as necessary.
Cardiac troponin increased	Grade 1 (Levels above the upper limit of normal and below the level of myocardial infarction as defined by the manufacturer) In subjects without symptoms suggestive of acute coronary syndrome	Perform additional troponin I testing by central laboratory, at 3 hours (± 1 hour) after initial local troponin test.  Follow institutional guidelines for management of detectable troponin testing.  Otherwise:  Repeat troponin testing at 3 (± 1 hour) after initial troponin test.  If levels at 3 hours (6 hours post-infusion) rise significantly, perform ECG in triplicate and repeat troponin testing 6 (± 1 hour) or 24 (± 1 hour) after initial troponin test.  If acute myocardial infarction is ruled out, continue U3-1402.  If acute myocardial infarction is confirmed, discontinue subject from U3-1402.
	Grade 3 (Levels consistent with myocardial infarction as defined by the manufacturer) In subjects without symptoms suggestive of acute coronary syndrome	Follow institutional guidelines for management of detectable troponin testing.  Perform 12-lead ECG in triplicate.  Perform additional troponin I testing by central laboratory at 6 and 12 hours (± 1 hour) after initial local troponin test.  Cardiologist consult as necessary.  If acute myocardial infarction is ruled out, resume U3-1402.  If acute myocardial infarction is confirmed, discontinue subject from U3-1402.

Table 5.2: Dose Delay Criteria and Dose Reduction for U3-1402 (Continued)

	Worst Toxicity NCI- CTCAE Version 5.0 Grade (unless otherwise specified)	Schedule Modification for U3-1402
	Grade 1 (Levels above the upper limit of normal and below the level of myocardial infarction as defined by the manufacturer) in subjects with symptoms suggestive of acute coronary syndrome	Repeat levels should be obtained every 6 to 8 hours to identify a rising and/or falling pattern of values.  Perform 12-lead ECG in triplicate.  Perform additional troponin I testing by central laboratory at 6 and 12 hours (± 1 hour) after initial local troponin test.  Follow institutional guidelines for management of detectable troponin testing.  Cardiologist consult as necessary.  If acute myocardial infarction is ruled out, resume U3-1402.  If acute myocardial infarction is confirmed, discontinue subject from U3-1402.
	Grade 3 (Levels consistent with myocardial infarction as defined by the manufacturer) in subjects with symptoms suggestive of acute coronary syndrome	Discontinue subject from U3-1402. Follow institutional guidelines for management of detectable troponin testing. Repeat levels should be obtained every 6 to 8 hours to identify a rising and/or falling pattern of values. Perform 12-lead ECG in triplicate. Perform additional troponin I testing by central laboratory at 6 and 12 hours (± 1 hour) after initial local troponin test. Cardiologist consult as necessary.
Electrocardiogram QT corrected interval prolonged	Grade 3 (Average QTcF ≥501 ms; >60 ms change from baseline)	Delay U3-1402 until resolved to ≤Grade 1 (QTcF ≤480 ms).  Determine if another medication the subject was taking may be responsible and can be adjusted or if there are any changes in serum electrolytes that can be corrected.  If QTcF prolongation is attributed to U3-1402, then reduce U3-1402 by 1 dose level.  Cardiologist consult as necessary.
	Grade 4 (Torsade de pointes; polymorphic ventricular tachycardia; signs/symptoms of serious arrhythmia)	Discontinue subject from U3-1402. Cardiologist consult as necessary

Table 5.2: Dose Delay Criteria and Dose Reduction for U3-1402 (Continued)

	Worst Toxicity NCI- CTCAE Version 5.0 Grade (unless otherwise specified)	Schedule Modification for U3-1402
Respiratory, thoracic and mediastinal disorders		
Pulmonary toxicity	See next column	If a subject develops radiographic changes potentially consistent with ILD/pneumonitis or develops an acute onset of new or worsening pulmonary or other related signs/symptoms such as dyspnea, cough or fever, rule out ILD/pneumonitis.
		If ILD/pneumonitis is suspected, delay U3-1402 dosing pending further evaluation and start corticosteroid treatment promptly unless clinically contraindicated.
		Evaluations must include CT (preferably high-resolution CT), and pulmonologist consultation (when the Investigator is not a pulmonologist). The following evaluations must also be obtained, as indicated:
		Infectious disease consultation as clinically indicated
		Blood culture and CBC (other blood tests could be considered as needed)
		Bronchoscopy and bronchoalveolar lavage if clinically indicated and feasible
		Pulmonary function tests
		• Pulse oximetry (SpO 2 )
		Arterial blood gases, as clinically indicated
		
 
Diffusing capacity of the lungs for carbon monoxide (DLCO), as clinically indicated
 

		
 
One blood sample collection for PK analysis as soon as ILD is suspected, if feasible
 

		Other tests, as clinically indicated
		If a noninflammatory/infectious etiology is confirmed by the Investigator, treat accordingly and resumption of U3-1402 may occur after discussion between the Investigator and Sponsor.
		All events of ILD regardless of severity or seriousness will be followed until resolution including after drug discontinuation.

Table 5.2: Dose Delay Criteria and Dose Reduction for U3-1402 (Continued)

	Worst Toxicity NCI- CTCAE Version 5.0 Grade (unless otherwise specified)	Schedule Modification for U3-1402
Pulmonary toxicity	Grade 1	The administration of U3-1402 must be delayed. U3-1402 can be restarted only if the event is fully resolved to Grade 0:
		
 
If resolved in ≤28 days from day of onset, maintain dose.
 

		• If resolved in >28 days from day of onset, reduce dose 1 level.
		Toxicity Management:
		
 
Monitor and closely follow-up in 2 to 7 days for onset of clinical symptoms and pulse oximetry.
 

		
 
Consider follow-up imaging in 1 to 2 weeks (or as clinically indicated).
 

		Consider starting systemic steroids (eg, at least 0.5-mg/kg/day prednisone or equivalent) until improvement, followed by gradual taper over at least 4 weeks.
		If worsening of diagnostic observations despite initiation of corticosteroids, then follow Grade 2 guidelines (if subject is asymptomatic, then subject must still be considered as Grade 1 even if steroid treatment is given).
	Grade 2	Permanently discontinue subject from study treatment. Toxicity Management:
		Promptly start systemic steroids (eg, at least 1-mg/kg/day prednisone or equivalent) for a minimum of 14 days or until complete resolution of clinical symptoms and chest CT findings, followed by gradual taper over at least 4 weeks.
		Monitor symptoms closely.
		Reimage as clinically indicated.
		
 
If worsening or no improvement in clinical or diagnostic observations in 5 days,
 

		
 
Consider increasing dose of steroids (eg, 2-mg/kg/day prednisone or equivalent) and administration may be switched to intravenous (eg, methylprednisolone).
 

		
 
Reconsider additional work-up for alternative etiologies as described previously.
 

		Escalate care as clinically indicated.

Table 5.2: Dose Delay Criteria and Dose Reduction for U3-1402 (Continued)

	Worst Toxicity NCI- CTCAE Version 5.0 Grade (unless otherwise specified)	Schedule Modification for U3-1402		
Pulmonary toxicity	Grade 3 or 4	Permanently discontinue subject from study treatment.		
1 dimonary toxicity	Grade 5 of 1	Toxicity Management:		
		Hospitalization is required.		
		Promptly initiate empiric high-dose methylprednisolone IV treatment (eg, 500-1000 mg/day for 3 days), followed by at least 1.0 mg/kg/day of prednisone (or equivalent) for a minimum of 14 days or until complete resolution of clinical symptoms and chest CT findings, followed by gradual taper over at least 4 weeks.		
		Reimage as clinically indicated.		
		If still no improvement within 3 to 5 days,		
		
 
Reconsider additional work-up for alternative etiologies as described above.
 
		
		
 
Consider other immuno-suppressants and/or treat per local practice.
 
		
Endocrine disorders				
Endocrine	Grade 3	Delay dose until resolved to ≤Grade 2, then:		
disorders		If resolved in ≤14 days, resume U3-1402.		
		If resolved in >14 days, U3-1402 may be resumed after discussion and agreement between the Investigator and Sponsor.		
	Grade 4	Discontinue subject from U3-1402.		
Eye disorders				
Ocular	Grade 3	Delay dose until resolved to ≤Grade 2, then: If resolved in ≤7 days, resume U3-1402.		
		If resolved in >7 days, then reduce U3-1402 by 1 dose level.		
		Ophthalmologist consultation as clinically indicated.		
	Grade 4	Discontinue subject from U3-1402. Ophthalmologist consult as necessary.		
Renal and urinary d	isorders			
Creatinine increased	Grade 3 (>3.0 × baseline; >3.0 - 6.0 × ULN)	Delay dose until resolved to ≤Grade 1 or baseline, then reduce U3-1402 by 1 dose level.		
	Grade 4 (>6.0 × ULN)	Discontinue subject from U3-1402.		

Table 5.2: Dose Delay Criteria and Dose Reduction for U3-1402 (Continued)

	Worst Toxicity NCI- CTCAE Version 5.0 Grade (unless otherwise specified)  Schedule Modification for U3-1402		
Hepatobiliary disord	lers		
AST or ALT increased without TBL increased	Grade 2 (>3.0 - 5.0 × ULN if baseline was normal; >3.0 - 5.0 × baseline if baseline was abnormal)	Continue U3-1402. In subjects without liver metastasis, monitor AST/ALT 24 to 72 hours later, and continue regular monitoring until resolution.	
	if baseline was normal; >5.0 - 20.0 × baseline if	Delay U3-1402 dose until resolved to ≤Grade 1, then: If resolved in ≤7 days, resume U3-1402. If resolved in >7 days, then reduce U3-1402 by 1 dose level.	
	>8.0-20.0 × ULN if baseline was normal; >8.0-20.0 × baseline level if baseline level was abnormal In subjects with liver metastases, if the baseline level was > 3 × ULN.	Delay U3-1402 dose until resolved to ≤baseline level, then:  If resolved in ≤7 days, resume U3-1402;  If resolved in >7 days, then reduce U3-1402 by 1 dose level.	
	Grade 4 (>20.0 × ULN if baseline was normal; >20.0 × baseline if baseline was abnormal)	Discontinue subject from U3-1402. Gastroenterologist or hepatologist consult as necessary.	
TBL increased	Grade 2 (>1.5 - 3.0 × ULN if baseline was normal; >1.5 - 3.0 × baseline if baseline was abnormal)	If no documented Gilbert's syndrome or liver metastases at baseline, delay U3-1402 until resolved to ≤Grade 1, then:  If resolved in ≤7 days, resume U3-1402;  If resolved in >7 days, reduce U3-1402 by 1 dose level.  If documented Gilbert's syndrome or liver metastases at baseline, continue U3-1402.	

Table 5.2: Dose Delay Criteria and Dose Reduction for U3-1402 (Continued)

	Worst Toxicity NCI- CTCAE Version 5.0 Grade (unless otherwise specified)	Schedule Modification for U3-1402
TBL increased	Grade 3 (>3.0-10.0 × ULN if baseline level was normal; >3.0-10.0 × baseline level if baseline level was abnormal)	
 
If no documented Gilbert's syndrome or liver metastases at baseline, delay U3-1402 dose until resolved to ≤Grade 1, then:
 
If resolved in ≤7 days, reduce U3-1402 by 1 dose level;
 
If resolved in >7 days, discontinue subject from U3-1402.
 

		If documented Gilbert's syndrome or liver metastases at baseline, delay U3-1402 dose until resolved to ≤Grade 2, then:  • If resolved in ≤7 days, reduce U3-1402 by 1 dose level;
		If resolved in >7 days, discontinue subject from U3-1402.
	Grade 4 (>10.0 × ULN if baseline was normal; >10.0 × baseline if baseline was abnormal)	Discontinue subject from U3-1402.
AST or ALT increased and TBL increased	AST or ALT ≥3 × ULN with simultaneous TBL >2 × ULN	Delay U3-1402 until drug-induced liver injury can be ruled out. The Investigator should consult with a gastroenterologist or hepatologist as needed, and the subject should be treated accordingly.  Monitor AST/ALT and TBL twice weekly until resolution or return to baseline.
		It is strongly recommended to perform a full diagnostic workup, to exclude alternative causes such as viral or autoimmune hepatitis, alcoholic liver injury, biliary tract disorders, or hemodynamic abnormalities. Results from diagnostic workup (including, for example: INR, direct bilirubin, serologic tests for hepatitis A, B, and C; alcohol use, ultrasound, MRI, CT scan, concomitant medication use, immunoglobulin levels, ECHO) must be recorded within the eCRF.  If drug-induced liver injury is ruled out, the subject
		should be treated accordingly, and resumption of U3-1402 may occur after discussion between the Investigator and Sponsor. U3-1402 will be permanently discontinued if drug induced liver injury cannot be ruled out from diagnostic workup.

Table 5.2: Dose Delay Criteria and Dose Reduction for U3-1402 (Continued)

	Worst Toxicity NCI- CTCAE Version 5.0 Grade (unless otherwise specified)	Schedule Modification for U3-1402
AST or ALT> 3.0 × ULN (if liver metastases are present, >5 × ULN) with known Hepatitis B and/or Hepatitis C infection at		Delay U3-1402 until reactivation of Hepatitis B and/or Hepatitis C can be ruled out.  Perform HBV DNA and/or HCV RNA to rule out reactivation of Hepatitis B and/or Hepatitis C, respectively.  Hepatologist and infectious disease consultations are recommended.
baseline		If reactivation of Hepatitis B and/or Hepatitis C is confirmed, permanently discontinue U3-1402.
Gastrointestinal diso	orders	
Nausea	Grade 3 (Inadequate oral caloric or fluid intake; tube feeding, TPN, or hospitalization indicated)	Delay U3-1402 until resolved ≤Grade 1, and consider treatment with antiemetics and/or corticosteroids as per Investigators judgement and local practice/guidelines, then:  If resolved to ≤Grade 1 in ≤14 days, resume U3-1402.  If does not resolve to ≤Grade 1 in >14 days, reduce U3-1402 by 1 dose level.
Vomiting	Grade 3 (Tube feeding, TPN, or hospitalization indicated)	Delay U3-1402 until resolved ≤Grade 1, and consider treatment with antiemetics and/or corticosteroids as per Investigators judgement and local practice/guidelines, then:  If resolved to ≤Grade 1 in ≤7 days, resume U3-1402.  If does not resolve to ≤Grade 1 in >7 days, reduce U3-1402 by 1 dose level.
	Grade ≥4	Discontinue subject from U3-1402

Based on currently available clinical safety data for U3-1402, it is recommended that patients receive premedication with antiemetic agents. Suggested agents include a 5-HT3 blocker in combination with another antiemetic or corticosteroid approximately 30 minutes prior to U3-1402 infusion. Choice of agents is based on Investigator's discretion as per local/institutional guidelines. Investigators must also consider providing patients with an antiemetic regimen for subsequent use as needed.

Table 5.2: Dose Delay Criteria and Dose Reduction for U3-1402 (Continued)

	Worst Toxicity NCI- CTCAE Version 5.0 Grade (unless otherwise specified)	Schedule Modification for U3-1402		
Diarrhea/ Colitis	Grade 3	Delay U3-1402 until resolved ≤Grade 1, and consider treatment per local practice/guidelines, then:  If resolved to ≤Grade 1 in ≤7 days, resume U3-1402.  If resolved to ≤Grade 1 in >7 days, then reduce U3-1402 by 1 dose level		
	Grade 4 (Life-threatening consequences; urgent intervention indicated)	Discontinue subject from U3-1402.		
Mucositis oral	Grade 3	Delay U3-1402 until resolved ≤Grade 1, and consider treatment per local practice/guidelines, then:		
		If resolved to ≤Grade 1 in ≤14 days, resume U3-1402; If resolved to ≤Grade 1 in >14 days, then reduce U3-1402 by 1 dose level.		
	Grade 4 (Life-threatening consequences; urgent intervention indicated)	Discontinue subject from U3-1402.		
Other Adverse Events (Nonlaboratory or Laboratory)	Grade 3	Delay U3-1402 until resolved ≤Grade 1 or baseline level, then:  If resolved in ≤7 days, resume U3-1402;  If resolved >7 days, then reduce U3-1402 by 1 dose level.		
	Grade 4 (Life-threatening consequences; urgent intervention indicated)	Discontinue subject from U3-1402.		

ALT = alanine aminotransferase; ANC = absolute neutrophil count; AST = aspartate aminotransferase; CT = computed tomography; ECG = electrocardiogram; ECHO = echocardiogram, eCRF = electronic case report form; g/dL = grams per deciliter; HBV DNA = hepatitis B virus DNA (a measure of the hepatitis B viral load in the blood); HCV DNA = hepatitis C virus DNA (a measure of the hepatitis C viral load in the blood); ILD = interstitial lung disease, INR = international normalized ratio; IV = intravenous; L = liter; LVEF = left ventricular ejection fraction; MRI = magnetic resonance imaging; NCI CTCAE = National Cancer Institute Common Terminology Criteria for Adverse Events; NSAIDs = nonsteroidal anti-inflammatory drugs; QTcF = corrected QT using Fridericia's formula; SpO2 = oxygen saturation of peripheral artery; TBL = total bilirubin; ULN = upper limit of normal.

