## **5.4.** Dose Interruptions and Reductions

Specific criteria for dose interruption, re-initiation, reduction and/or discontinuation of U3-1402 are listed in Table 5.2. Doses may also be interrupted for other AEs per Investigator discretion, and supportive therapy may be administered in accordance with local practice guidelines. All dose interruptions or dose modifications must be recorded on the AE and drug administration eCRF pages.

Dose modifications are applicable only to TEAEs that are assessed as related to use of U3-1402 by the Investigator(s). For non-drug-related TEAEs, follow standard clinical practice. Appropriate external experts such as a cardiologist, pulmonologist, etc, should be consulted as deemed necessary.

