### Dose Reduction(s) for Q3W Dosing Schedule

If dose reduction is required, U3-1402 dosing should be reduced by 1 dose level at a time (Table 5.1). Once the dose of U3-1402 has been reduced due to an AE, all subsequent cycles should be administered at that lower dose level unless further dose reduction is required.

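### Table 5.2, QTc Grade 3 row: the release number (QTcF at or below 480 ms) ignores the change-from-baseline limb of the hold, so for baselines below 420 ms one ECG can meet both

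*Combined protocol and SAP*

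**What the plan says.** The QTc row of Table 5.2 (combined protocol, Section 5.4.2) defines the event that stops dosing as "Grade 3 (Average QTcF ≥501 ms; >60 ms change from baseline". The action column then says "Delay U3-1402 until resolved to ≤Grade 1 (QTcF ≤480 ms". It asks the site to look for a responsible co-medication or a correctable electrolyte change, to consult a cardiologist as necessary, and adds: "If QTcF prolongation is attributed to U3-1402, then reduce U3-1402 by 1 dose level".

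Four other places bear on the row:

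- Section 5.4 confines dose modifications to treatment-emergent events that the Investigator judges related to U3-1402, and also lets Investigators interrupt dosing at their discretion.
- For the Q3W schedule, Section 5.4.2 makes a reduction permanent: "all subsequent cycles should be administered at that lower dose level unless further dose reduction is required".
- The column heading refers grading to NCI-CTCAE version 5.0 unless otherwise specified. The documents do not reproduce those definitions.
- Section 8.3.1 names QT prolongation among the cardiac adverse events of special interest.

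I found no other section that adds a baseline-relative condition for resuming after a QTc hold.

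**The concern.** A hold rule and its release rule should not both be satisfied by the same measurement. Here the trigger has an absolute limb and a baseline-relative limb, and the number in the release addresses only the absolute one. A subject with a modest baseline can be held for a rise of more than 60 ms while the QTcF is already at or below 480 ms.

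The row does not say whether the parenthesis defines the release grade or adds to it. In the toxicity column of Table 5.2, a parenthesis after a grade normally says what that grade is, so a site may reasonably take 480 ms as the test. This is also the only row that puts a number beside its release grade. The closest parallel, creatinine Grade 3, pairs a baseline-relative and an absolute limit in the same way but releases on grade or return to baseline, with no figure attached.

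At stake is consistent handling of a named cardiac risk: two sites, each able to point to the same row, could act differently on the same ECG.

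**Working it through.** The plan states no figure for this point, so there is none to reproduce. The check compares the two rules directly.

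**Inputs**

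- Hold trigger, Table 5.2: QTcF at or above 501 ms, or more than 60 ms above baseline.
- Release number, Table 5.2: QTcF at or below 480 ms.
- Baseline, Section 11.1: last non-missing value before first dose. The row does not define baseline, so using this definition is an assumption.
- Eligibility, Sections 4.2.1 and 4.2.3: mean screening QTcF above 450 ms (men) or 470 ms (women) is excluded. There is a ceiling and no floor, so baselines below 420 ms are admissible.

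**How to read the semicolon.** The next row for the same event, QTc Grade 4, uses semicolons to list alternatives (torsade de pointes, polymorphic ventricular tachycardia, signs or symptoms of serious arrhythmia). The two limbs of Grade 3 are therefore best read as joined by *or*.

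**Overlap.** Let b be baseline and x the on-treatment QTcF.

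- The change limb holds if x > b + 60.
- The release number is met if x ≤ 480.
- Both are true when b + 60 < x ≤ 480.
- This range is non-empty when b + 60 < 480, that is, b < 420. Its width is 480 − (b + 60) = 420 − b ms.

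The absolute limb cannot overlap, because 501 exceeds 480.

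| Baseline (ms) | Whole-ms QTcF meeting both hold and release number | Values (420 − b) |
|---|---|---|
| 380 | 441–480 | 40 |
| 400 | 461–480 | 20 |
| 410 | 471–480 | 10 |
| 415 | 476–480 | 5 |
| 419 | 480 | 1 |
| 420 | none (480 − 420 = 60, not more than 60) | 0 |

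The row uses an average QTcF, which need not be a whole number, so the exact limit is a baseline below 420 ms; in whole milliseconds that is 419 or less.

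**Proposed rule.** Release when x ≤ 480 and x ≤ b + 60. The first condition excludes x ≥ 501 and the second excludes x > b + 60, so no ECG can meet both hold and release at any baseline. The release limit becomes the smaller of 480 and b + 60: 460 ms at a baseline of 400, and 480 ms, as now, for every baseline of 420 or more.

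**The case against.** The best defence is that the operative instruction is resolution to Grade 1 or lower. An ECG still more than 60 ms above baseline is Grade 3 by the same row, so it has not resolved, whatever the parenthesis says. If the parenthesis adds to the grade, there is no conflict. That is a fair reading and probably the intended one. It does not dispose of the point, because the row does not say so and parentheses after grades elsewhere in the table are definitions.

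The defence also narrows the consequence, and this part stands. Many ECGs in Table 6.1 fall when no dose is due, so same-day redosing can arise only on a pre-dose ECG. An isolated ECG abnormality must first qualify as an adverse event under Section 8.2, and must be judged related under Section 5.4. Investigator discretion to interrupt remains.

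Two stronger conclusions are tempting, and the documents support neither.

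- A reader might infer that the semicolon could mean *and*, so that a QTcF of 501 ms or more goes unheld at high baselines. Semicolon use in Table 5.2 is admittedly not uniform: the infusion reaction row lists joint descriptors ("Mild transient reaction; infusion interruption not indicated; intervention not indicated"), while the ejection fraction rows write the connective out ("LVEF <40% or >20% drop from baseline"; "LVEF 40% to ≤45% and decrease is ≥10% to 20% (absolute value) from baseline"). But the first is a prose description of one mild reaction, the ejection fraction rows carry no grade label, and the adjacent QTc Grade 4 row plainly lists alternatives. Even under *and*, only values from 501 ms to baseline + 60 would escape, and only at baselines of 441 ms or more in whole milliseconds.
- A reader might infer that subjects could be redosed at an unchanged dose. Because these modifications apply only to events judged related, the one-level reduction would normally apply as well.

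**Conclusion.** The point holds as a minor correction to a safety rule. With the trigger read as *or*, the release number can be met by an ECG that is still Grade 3 by the same row, for any baseline below 420 ms, over a range 420 − b ms wide. The exposed case is resumption one dose level lower (6.4 to 4.8 mg/kg, or 4.8 to 3.2 mg/kg in Table 5.1) sooner than the grade alone would allow, with the medication and electrolyte review and cardiologist consult still in place.

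This rests on three assumptions: the limbs are alternatives, baseline is the last pre-dose value, and a site treats the number as the release test. If the site treats the number as additional to the grade, the conflict disappears.

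How many subjects this touches cannot be derived: the documents give neither the baseline QTcF distribution nor the frequency of rises above 60 ms. No endpoint, sample size or error rate is affected.

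**What to change.** Rewrite the one row of Table 5.2:

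- Trigger: *average QTcF ≥501 ms or >60 ms above baseline*.
- Release: *only when QTcF is ≤480 ms and no longer >60 ms above baseline*, or at a stricter value if the sponsor's safety physicians prefer one.
- Keep the one-level reduction, the medication and electrolyte review and the cardiologist consult as they are.

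No scheduled ECGs are added, because Table 6.1 already provides triplicate recordings at screening and before dosing. The cost is that some holds in subjects with baselines below 420 ms will lengthen. A few may reach the 4-week delay limit in Section 5.4.1, at which point withdrawal may be considered after discussion between Investigator and Sponsor. For baselines of 420 ms or more the release limit stays at 480 ms.
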